10.1 Demographic Variables

The demographic variables collected in this study include age, sex, ethnicity, race, whether the subject is Japanese, if the subject's parents or grandparents are of Japanese descent, height, and weight. Subjects who record more than one race will be grouped into a single category denoted as Multiple. Demographic variables will be summarized for the ITT and safety populations, separately.

Age (years) will be summarized, overall and by treatment, using continuous descriptive statistics. Age will also be categorized as follows: < 65 years and \geq 65 years. Age will be reported in years and calculated using the following formula:

$$\text{Age} = (\text{Informed Consent Date} - \text{Date of Birth}) / 365.25, \text{ truncated as an integer}$$

The number and percentage of subjects will be presented, overall and by treatment, for age category, sex, race, ethnicity, age, sex, ethnicity, race, ethnic Japanese, Japanese descent, and stratification category.

A subject listing that includes all demographic variables will be provided.

10.2 Pretreatment Variables

Baseline disease characteristics will be summarized, overall and by treatment, for the ITT and safety populations using continuous descriptive statistics for inferior corneal staining score; ocular discomfort score; unanesthetized Schirmer's test value; TFBUT; fluorescein staining score (Ora Calibra[®] scale) in the regions: central, superior, inferior, temporal, corneal sum, conjunctival sum and total eye score; lissamine green staining by region: central, superior, inferior, temporal, nasal, and conjunctival sum as assessed by the Ora Calibra[®] Corneal and Conjunctival Staining Scale; [REDACTED] The scale for each assessment is provided in the variables' respective subsection in Section 13 and Section 15 of this SAP.

11. Medical History and Concomitant Medications

11.1 Medical History

Medical history will be coded using the Medical Dictionary for Regulatory Activities (MedDRA) 22.0.

Ocular and non-ocular medical history will be summarized using discrete summary statistics and presented by treatment and overall at the subject level by System Organ Class (SOC) and Preferred Term (PT) using the safety population. If a subject reports the same PT multiple times within the same SOC, that PT will only be reported once within that SOC. As with the PT, if a subject reports multiple conditions within the same SOC, that SOC will only be reported once. SOCs are listed in alphabetical order; PTs within a SOC are listed in order of descending frequency across all subjects.

Listings of medical history will be generated separately for ocular and non-ocular data.

11.2 Concomitant Medications

Ocular and non-ocular concomitant medications will be coded using the World Health Organization Drug Dictionary (WHODrug) Global (B3, March 2019) and summarized to the therapeutic drug class (Anatomical Therapeutic Chemical [ATC] 4 classification) and preferred name. If the ATC 4 classification is not provided, then the next lowest classification that is provided in the coding dictionary will be used. The preferred name will be defined as the active ingredient; if the active ingredient is not provided or includes more than two ingredients (e.g., multivitamins), then the drug name will be summarized as the preferred name. Any uncoded terms will be summarized under the ATC classification and preferred name of "Uncoded."

Concomitant medications are defined as those medications listed as having been taken (1) prior to initiation of study drug administration and continuing for any period of time following the first administration of study drug or (2) at any time following the first administration of study drug. Prior medications are reported medications that have been taken prior to initiation of study drug administration but not during the study.

Concomitant medications will be summarized using the ITT population. Medications will be tabulated for each treatment group using frequencies and percentages. Subjects may have more than one medication per ATC text. At each level of subject summarization, a subject will be counted once if he/she reports one or more medications. Percentages will be based on the number of subjects in each treatment group. Listings of prior and concomitant medications will be generated separately for ocular and non-ocular data.

12. Dosing Compliance and Treatment Exposure

12.1 Dosing Compliance

Dosing compliance (% compliance) will be assessed by calculating the number of actual doses received and comparing that to the number of expected doses as follows:

$$\text{Compliance (\%)} = \frac{\text{Number of Actual Doses Received}}{\text{Number of Expected Doses}} \times 100\%$$

The number of actual doses received will be recorded in the eCRF and determined through the in-office instillations. The number of expected doses that will be used for calculating compliance will be calculated as follows:

- For subjects in [REDACTED] dosing group: $4 \times \{[\text{Date of Study Completion/Discontinuation} - \text{Date of Visit 2 (Day 1)}]\} - 1 \times [\text{number of visits attended in (Visit 2, Visit 3, Visit 4)}]$
- For subjects in [REDACTED] dosing groups: $2 \times \{[\text{Date of Study Completion/Discontinuation} - \text{Date of Visit 2 (Day 1)}]\}$

If a randomized subject discontinues from the study on Day 1, the number of expected doses will be 1.

A categorical dosing compliance variable will also be derived as non-compliant (<80%), compliant ($\geq 80\%$ and $\leq 125\%$), and over compliant ($>125\%$).

Dosing compliance (%) will be summarized with continuous descriptive statistics for each treatment group using the safety population. The compliance category defined above will be summarized with discrete summary statistics.

A subject listing of dosing compliance will also be produced.

A subject listing of run-in, run-in instillation, and run-in replacement will be produced.

A subject listing of study drug assignment, study drug instillation, and study drug replacement will be produced.

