4 OVERALL STUDY DESIGN

This is a Phase 2, multicenter, randomized, double-masked, vehicle-controlled, parallel-group design with block enrollment. Subjects will be randomized to one of the following treatment groups at Visit 2:

- [REDACTED] K-161; [REDACTED] (N=~60)
- [REDACTED] K-161; [REDACTED] (N=~60)
- [REDACTED] K-161; [REDACTED] (N=~60)
- Placebo Ophthalmic Solution (Vehicle); [REDACTED] (N=~60)

Approximately 240 subjects will be randomly assigned to one of the four treatment groups (1:1:1:1). [REDACTED]

[REDACTED] Subjects, Sponsor, Contract research organization (CRO), and site personnel will be masked to treatment assignment. To ensure masking, a dedicated unmasked staff member/technician will be delegated to dispense and observe instillation of randomized study drug and collect randomized study drug from a subject for drug accountability. This person cannot perform any other study-related procedures. Additionally, the informed consent form (ICF) will not indicate any relationship between dosing regimen and treatment. Subjects will be instructed not to discuss their assigned dosing regimen or perceived treatment effects with other study participants.

During the screening period, two 90-minute exposures to the CAE will be conducted to ascertain eligibility to enter the study. Subjects who qualify after the initial screening visit will enter the run-in phase, where they will self-administer vehicle [REDACTED] for approximately 14 days. Those who qualify at Visit 2 (Day 1) will be randomized to receive study drug in a double-masked fashion for 28 days. Randomization will be stratified on Visit 2 Post-CAE inferior fluorescein staining and

Post-CAE ocular discomfort on the Ora Calibra® scale. Subjects will self-administer drops either [redacted] or [redacted]

At Visit 4 (Day 15) and Visit 5 (Day 29), CAE exposure will occur, with pre-CAE, during CAE (symptoms only) and post-CAE assessments of ocular signs and symptoms. At Visit 3, no CAE exposure will occur but signs and symptoms will be assessed. Study drug will be discontinued at Visit 5. Subjects will exit from the study at this visit. The follow-up phone call will occur about 7 days after the final day of randomized study drug treatment.

The timing of subject visits and examinations will be consistent throughout the study.

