8.3.4 Visit 3: Day 8 ±1

- Study Drug Collection by unmasked staff member
- Medical/medication history update
- AE Query
- Ora Calibra® Ocular Discomfort Scale
- Ora Calibra® Ocular Discomfort & 4-Symptom Questionnaire
- OSDI® Questionnaire
- Visual Analog Scale (VAS)

- Conjunctival Redness

- Blink Rate
- Tear Osmolarity
- TFBUT
- Fluorescein Staining
- Lissamine Green Staining
- At least 15-minute wait between lissamine green staining and Schirmer's test
- Schirmer's Test
- Study Drug Kit Dispensation: Prior to discharge from the study site on Visit 3, subjects will be assigned a new study drug kit via the IWRS system for at-home dosing up to Visit 4.
- Subject Instructions Dispensation

8.3.5 Visit 4: Day 15 ± 2

- Study Drug Collection by unmasked staff member
- Medical/medication history update
- AE query
- Ora Calibra® Ocular Discomfort Scale
- Ora Calibra® Ocular Discomfort & 4-Symptom Questionnaire
- OSDI^c Questionnaire
- Visual Analog Scale (VAS)

— [REDACTED]

■

- Conjunctival Redness
- Blink Rate
- Tear Osmolarity
- TFBUT

- Fluorescein Staining
- Lissamine Green Staining
- At least 15-minute wait between lissamine green staining and Schirmer's test
- Schirmer's Test

■ [REDACTED]
■ [REDACTED]
■ [REDACTED]
■ [REDACTED]

- Ora Calibra® Ocular Discomfort Scale
- Ora Calibra® Ocular Discomfort & 4-Symptom Questionnaire
- Visual Analog Scale (VAS)

■ [REDACTED]

- Conjunctival Redness
- TFBUT
- Fluorescein Staining
- Lissamine Green Staining
- Study Drug Kit Dispensation: Prior to discharge from the study site on Visit 4, subjects will be assigned a new study drug kit via the IWRS system for at-home dosing up to Visit 5.
- Subject Instructions Dispensation

■ [REDACTED]
■ [REDACTED]

- AE Query
- Subjects will be scheduled for Visit 5.

8.3.6 Visit 5: Day 29 ± 2

- Study Drug Collection by unmasked staff member
- Medical/medication history update
- AE query
- [REDACTED]
- [REDACTED]
- Ora Calibra® Ocular Discomfort Scale
- Ora Calibra® Ocular Discomfort & 4-Symptom Questionnaire
- OSDI® Questionnaire
- Visual Analog Scale (VAS)
- [REDACTED]
- [REDACTED]
- Conjunctival Redness
- Blink Rate
- Tear Osmolarity
- [REDACTED]
- TFBUT
- Fluorescein Staining
- Lissamine Green Staining
- At least 15-minute wait between lissamine green staining and Schirmer's test
- Schirmer's Test
- [REDACTED]
- Ora Calibra® Ocular Discomfort Scale
- Ora Calibra® Ocular Discomfort & 4-Symptom Questionnaire
- Visual Analog Scale (VAS)
- [REDACTED]
- [REDACTED]

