8.5 Compliance with Protocol

Subjects will be given written instructions; instructed on proper instillation; and instructed on proper storage of the IP at the end of Visits 1, 2, 3, and 4. The subject used/unused [REDACTED] will be collected at each visit from Visit 2 up to and including Visit 5 to assess dosing compliance. Dosing compliance will be based on [REDACTED]. If the subject is less than 80% or more than 125% compliant with dosing based on [REDACTED], then the subject will be deemed non-compliant and a dosing deviation should be recorded in the source document. The investigator will use these guidelines to determine subject study compliance and deviation compliance.

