20. Tables.....	49			
21. Listings	54			
22. Figures	55			

List of Abbreviations

ADaM	Analysis Data Model
AE	Adverse Event
ANCOVA	Analysis of Covariance
ATC	Anatomical Therapeutic Chemical
CI	Confidence Interval
CRO	Clinical Research Organization
CS	Clinically Significant
DMP	Data Management Plan
eCRF	Electronic Case Report Form
IB	Investigator's Brochure
ICF	Informed Consent Form
ICH	International Conference on Harmonisation
ITT	Intent-to-Treat
IWRS	Interactive Web Response System
LOCF	Last Observation Carried Forward
LS	Least Squares
MCMC	Markov Chain Monte Carlo
MedDRA	Medical Dictionary for Regulatory Activities
NCS	Not Clinically Significant
ODS	Ocular Discomfort Score
OSDI [®]	Ocular Surface Disease Index
OU	Oculus uterque (Both Eyes)
PDF	Portable Document Format
PP	Per Protocol
PT	Preferred Term
RTF	Rich Text Format
SAE	Serious Adverse Event
SAP	Statistical Analysis Plan
SDC	Statistics & Data Corporation
SDTM	Study Data Tabulation Model
SE	Standard Error
SOC	System Organ Class
TEAE	Treatment-Emergent Adverse Event
TFBUT	Tear Film Break-Up Time
TMF	Trial Master File

WHODrug

World Health Organization Drug Dictionary

1. Introduction

The purpose of this statistical analysis plan (SAP) is to describe the planned analyses and reporting for protocol K-161-2.01US / [REDACTED] Amendment 2 dated 26JUL2019

This SAP is being written with due consideration of the recommendations outlined in the most recent International Conference on Harmonisation (ICH) E9 Guideline entitled Guidance for Industry: Statistical Principles for Clinical Trials and the most recent ICH E3 Guideline, entitled Guidance for Industry: Structure and Content of Clinical Study Reports.

This SAP describes the data that will be analyzed and the subject characteristics, efficacy, and safety assessments that will be evaluated. This SAP provides details of the specific statistical methods that will be used. The statistical analysis methods presented in this document will supersede the statistical analysis methods described in the clinical protocol. If additional analyses are required to supplement the planned analyses described in this SAP, they may be completed and will be identified in the clinical study report.

2. Study Objectives

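### SAP 12.1 counts only clinic instillations as doses received but divides by every scheduled dose, so the planned compliance percentages cannot be interpreted

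*SAP*

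**What the plan says.** SAP 12.1 defines compliance as actual doses over expected doses, times 100. On the numerator it says: "The number of actual doses received will be recorded in the eCRF and determined through the in-office instillations". The denominator takes the days from Visit 2 to study completion or discontinuation. In one dosing group it multiplies these by 4 and subtracts one dose for each of Visits 2, 3 and 4 attended. In the other groups it multiplies them by 2. Results below 80% are non-compliant, 80% to 125% compliant, and above 125% over-compliant. The percentage and the category are summarised by arm in the safety population, and a subject listing is planned.

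Treatment is mainly self-administered. Protocol 4 says: "Those who qualify at Visit 2 (Day 1) will be randomized to receive study drug in a double-masked fashion for 28 days". At Visit 3, Protocol 8.3.4 says "subjects will be assigned a new study drug kit via the IWRS system for at-home dosing up to Visit 4".

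Protocol 8.5 names a different source. The subject's used and unused product (the unit is redacted) "will be collected at each visit from Visit 2 up to and including Visit 5 to assess dosing compliance", with the same limits of 80% and 125%. SAP 1 says: "The statistical analysis methods presented in this document will supersede the statistical analysis methods described in the clinical protocol". SAP 18, which lists departures from the protocol's analyses, mentions only the data handling for OCT and strip meniscometry.

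**The concern.** The numerator and denominator cover different sets of doses. The first is the handful instilled at the site; the second is every dose scheduled over about four weeks. Their ratio does not measure adherence. It measures roughly how many clinic doses were given relative to regimen and time on study.

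Two consequences follow. A subject who takes every dose is labelled non-compliant. And because the clinic count should be similar in every arm while the denominator nearly doubles with the four-a-day schedule, the arms would appear to differ in compliance even if adherence were identical. Optimum dosage and dosing regimen are among the study objectives, so a reader comparing regimens would want a usable compliance figure for each arm.

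**Working it through.** The documents print no expected-dose count, so there is no stated figure to reproduce. The check evaluates the SAP 12.1 formulas directly.

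**Inputs**
- Days from Visit 2 (Day 1) to Visit 5 (Day 29): 28. With the ±2-day window (Day 27 to Day 31): 26 to 30.
- Visits 2, 3 and 4 all attended: subtract 3 in the four-a-day formula.
- Clinic doses of randomised drug per subject: not visible. Protocol 7.1.3 has the unmasked technician observe instillation, so some occur. Assumption: 3 (one at each dispensing visit: 2, 3 and 4), with a range of 1 to 5.

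**Expected doses at Day 29**
- Four-a-day: 4 × 28 − 3 = 109
- Two-a-day: 2 × 28 = 56

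**Compliance under the rule as written (clinic doses ÷ expected doses)**

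| Clinic doses | Four-a-day (109) | Two-a-day (56) |
|---|---|---|
| 1 | 0.9% | 1.8% |
| 3 | 2.8% | 5.4% |
| 5 | 4.6% | 8.9% |

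Across the Visit 5 window, expected doses run from 101 to 117 and from 52 to 60. The highest score for any completer is then 5/52 = 9.6%.

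**Doses needed to reach 80%**
- 0.8 × 109 = 87.2, so 88 doses
- 0.8 × 56 = 44.8, so 45 doses

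No plausible number of clinic instillations comes near either figure.

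**Artefact between regimens.** With the same clinic count in each arm, the ratio of the two scores is 109/56 = 1.95, whatever that count is.

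**Inversion.** SAP 12.1 sets expected doses to 1 for a subject who leaves on Day 1. If that subject had one clinic dose (assumed), compliance is 1/1 = 100%. A perfectly adherent completer is classed non-compliant while a Day 1 dropout is classed compliant.

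**Sensitivity to the end date.** Protocol 4 has subjects exit at Visit 5, but Protocol 8.3.7 and Appendix 1 put study exit at the Day 36 call. With Day 36 as the completion date, expected doses are 4 × 35 − 3 = 137 and 2 × 35 = 70. Three clinic doses then give 3/137 = 2.2% and 3/70 = 4.3%, so the conclusion is unchanged. The end date does matter once the numerator is corrected: a subject who took every dose to Day 29 would score 109/137 = 79.6% (non-compliant) or 56/70 = 80.0% (exactly on the limit).

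**The case against.** The best defence is that the sentence is incomplete rather than a deliberate choice. The denominator plainly counts home doses, so overall adherence must be intended. The eCRF may hold home-dose counts, and Listing 16.2.5.4 covers drug accountability. A programmer who saw about 3% for everyone would stop and ask. Much of this is fair: a drafting slip is the likeliest explanation, and literal output would probably be noticed. But saying where a count is recorded does not say how home doses are counted, and SAP 12.1 does not draw on the accountability listing. A repair made at programming would follow a rule that nobody had specified in advance.

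Redaction is the second defence. The clinic-dose count and the unit in Protocol 8.5 are blacked out, so the 3 is an assumption. That stands, and it is why a range is shown; the result holds throughout it. The numerator sentence carries no redaction mark, although unmarked loss of text cannot be wholly excluded.

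The clause by which the SAP supersedes the protocol should not be pressed too far. It covers statistical methods. Collecting product and accounting for it are trial procedures and remain in force.

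A reader might also infer that the error empties the per-protocol set, since Protocol 8.5 makes dosing outside 80% to 125% a deviation and significant deviations exclude subjects. The documents do not support this. The Protocol 8.5 deviation rests on collected product and is noted in source documents. Per-protocol membership depends on significant deviations and study completion, assessed before database lock and unmasking (SAP 7.2), and SAP 9 has deviations judged major or minor in a masked review. Nothing links the SAP 12.1 category to either step.

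**Conclusion.** The point holds: the compliance rule is wrong as written, not merely short of detail. It gives every completer a score below 10% against a limit of 80%, and a spurious difference of about 1.95-fold between regimens. It also conflicts with Protocol 8.5 without being declared in SAP 18. This rests on completion within the Visit 5 window, attendance at Visits 2 to 4, and 1 to 5 clinic doses per subject, similar across arms.

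The reach is limited to the compliance summary and its categories in the safety population, and the compliance listing. The primary and secondary efficacy analyses do not use this variable, and no effect on the per-protocol set can be shown. It should be corrected before database lock, but it does not threaten the trial's main conclusions.

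**What to change.** Reconcile SAP 12.1 with Protocol 8.5:

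- **Numerator:** home doses derived from the used and unused product returned at Visits 3, 4 and 5, plus in-office instillations of randomised drug. Product collected at Visit 2 is run-in vehicle and should not count.
- **End date:** stop both numerator and denominator at the last date of randomised dosing (Visit 5 or earlier discontinuation), not at the Day 36 call. Protocol 5.5 lets subjects stop study drug and stay in the study, so the SAP should state which date applies to them.
- **Conversion:** state how returned units are turned into doses.
- **SAP 18:** if any departure from Protocol 8.5 is intended, declare it there.

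A fully adherent Day 29 completer would then score 109/109 or 56/56, that is 100%.

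The cost is a short edit to SAP 12.1. No new visits or procedures are needed, because product is already collected and accounted for by the unmasked technician. The small downside is that the conversion must be agreed and the accountability data must be available to the compliance dataset. Whether the eCRF captures them in a form that yields doses cannot be seen from the public documents and should be confirmed.

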12.2 Treatment Exposure

Extent of treatment exposure for completed or discontinued subjects will be calculated in days using the following:

$$\text{Extent of Exposure (days)} = (\text{Date of Study Completion/Discontinuation} - \text{Date of Visit 2 (Day 1)})$$

If a randomized subject discontinues from the study on Day 1, the extent of exposure will be 1 day.

Extent of treatment exposure for subjects who were lost to follow-up will be calculated in days using the following:

$$\text{Extent of Exposure (days)} = (\text{Date of Last Recorded Visit} - \text{Date of Visit 2 (Day 1)}) + 1$$

Extent of treatment exposure for each subject exposed to study drug will be summarized with continuous descriptive statistics for each treatment group using the safety population. A subject listing of treatment exposure will also be produced.

13. Efficacy Analyses

13.1 Primary Analysis

The primary efficacy endpoints of the study are:

- Mean change from baseline in post-CAE® inferior corneal fluorescein staining score on the Ora Calibra® scale at Visit 5 (Day 29), comparing [REDACTED] K-161 [REDACTED] to vehicle [REDACTED]
- Mean change from baseline in post-CAE® ocular discomfort scale on the Ora Calibra® scale at Visit 5 (Day 29), comparing [REDACTED] K-161 [REDACTED] to vehicle [REDACTED]

Change from baseline for both endpoints will be calculated as Visit – Baseline, where a positive difference indicates a worsening of dry eye signs or symptoms and a negative difference indicates an improvement of dry eye signs or symptoms. Treatment comparisons between [REDACTED] K-161 [REDACTED] and vehicle [REDACTED] will be calculated as [REDACTED] K-161 [REDACTED] - vehicle [REDACTED]. All primary endpoints will be described in subject listings.

13.1.1 INFERIOR CORNEAL FLUORESCEIN STAINING SCORE AT VISIT 5 (DAY 29) POST-CAE, [REDACTED] K-161 [REDACTED] VS VEHICLE [REDACTED]

Fluorescein staining will be conducted at all visits at pre-CAE® and post-CAE®. Grading will be conducted using the Ora Calibra® Scale from 0 to 4 with the use of half grade (0.5) increments, where grade 0 = None and 4 = Severe. The regions to be assessed will be the central, superior, inferior, temporal, nasal, corneal sum, conjunctival sum, and total eye score for study eye only.

Inferior corneal fluorescein staining will be summarized at Visit 5 (Day 29) Post-CAE® by treatment groups using continuous descriptive statistics. Primary analysis will use an analysis of covariance (ANCOVA) model adjusted for baseline value, site, and with treatment group as the explanatory variable. Changes from baseline for each treatment group in inferior corneal fluorescein staining will be compared between [REDACTED] K-161 [REDACTED] and vehicle [REDACTED]. In addition, treatment by baseline and treatment by study site interactions will be explored in separate models to evaluate how the treatment effect may differ for baseline value and study sites. Analyses will be performed by baseline stratification (≤ 3.0 and >3.0) and/or site to understand how the treatment effect differs for baseline value and study sites. Least squares (LS) means for each treatment group and the LS mean difference between treatment groups will be presented from the models together with standard errors (SE), two-sided p-values, and two-sided 95% CIs.

For the primary analysis, the primary efficacy endpoint of inferior corneal fluorescein staining will have missing data imputed using a control-based pattern mixture model under the assumption of a missing not at random mechanism. The imputation will first impute non-monotone missing data using MCMC to obtain a dataset with a monotone missing pattern, then a control-based pattern mixture model will be run. The SAS® code for obtaining multiple pattern mixture model imputation data is:

```

PROC MI DATA = INDATA SEED = 6849548 OUT = MDATA NIMPUTE = 100
      MINIMUM = 0 MAXIMUM = 4 ROUND = 0.5;
      BY TREATMENT;
      MCMC IMPUTE=MONOTONE;
      VAR BASELINE IFS4 IFS5;
      RUN;
  
```

```

PROC MI DATA = MDATA SEED = 3541655 OUT = OUTDATA NIMPUTE = 1
  
```

```

        MINIMUM = . 0 0 0 MAXIMUM = . 4 4 4 ROUND = . 0.5 0.5 0.5;
        BY _Imputation_;
        CLASS TREATMENT;

        MONOTONE REG(IF54 = BASELINE/ DETAILS);
        MONOTONE REG(IF55 = BASELINE IF54/ DETAILS);
        MNAR MODEL(IF54 IF55 / MODELOBS=(TREATMENT='Vehicle'));
        VAR BASELINE IF54 IF55;
RUN;

```

where

- *INDATA* is the name of the input dataset
- *MDATA* is the name an intermediary dataset with a monotone missing pattern
- *OUTDATA* is the name of the output dataset
- *TREATMENT* is the name of the treatment group variable
- *BASELINE* is the baseline inferior corneal fluorescein staining
- *IF54-IF55* are the inferior corneal fluorescein staining at Visits 4 (Day 15) through Visit 5 (Day 29)

If multiple pattern mixture model imputation fails to generate imputations, baseline total sum fluorescein staining score will be added to the `VAR` statement and multiple imputation will be reattempted. If multiple imputation still fails to generate the required imputation, then `MINIMUM`, `MAXIMUM`, and `ROUND` statements will be removed.

After the imputed data sets are obtained, the following code will be used to execute the ANCOVA model on each imputed data set and the results combined from the analyses:

```

PROC MIXED DATA = OUTDATA;
    BY _IMPUTATION_;
    CLASS TREATMENT SITE;
    MODEL CHG = BASELINE TREATMENT SITE/ SOLUTION COVB;
    LSMEANS TREATMENT / CL PDIFF;
    ODS OUTPUT LSMEANS = OUTLS DIFFS = OUTDIFFS;
RUN;

PROC SORT DATA=OUTLS; BY TREATMENT _IMPUTATION_; RUN;
PROC MIANALYZE DATA=OUTLS;
    BY TREATMENT;
    MODELEFFECTS ESTIMATE;
    STDERR STDERR;
RUN;

DATA OUTDIFFS;
    SET OUTDIFFS;
    COMPARISON = TREATMENT||' - '||LEFT(_TREATMENT);

```

```

RUN;

PROC SORT DATA=OUTDIFFS; BY COMPARISON _IMPUTATION_; RUN;
PROC MIANALYZE DATA=OUTDIFFS;
  BY COMPARISON;
  MODELEFFECTS ESTIMATE;
  STDERR STDERR;
RUN;

```

where

- *TREATMENT* is the name of the treatment group variable
- *BASELINE* is the baseline inferior corneal fluorescein staining
- *CHG* is the change from baseline of the inferior corneal fluorescein staining at Visit 5 (Day 29) – *BASELINE*
- *SITE* is the site ID
- *OUTLS* is the name of the output dataset that contains the statistical results for the treatment mean from the ANCOVA model that is run on each of the 100 imputation datasets
- *OUTDIFFS* is the name of the output dataset that contains the statistical results for the difference in treatment mean from the ANCOVA model that is run on each of the 100 imputation datasets

Two sample t-tests will use similar SAS code to execute pattern mixture model multiple imputation analysis.

Sensitivity analyses will also include using ITT population with observed data only and ITT population with last observation carried forward (LOCF).

Markov chain Monte Carlo (MCMC) imputation with the ITT population will be used for sensitivity analysis under the assumption of a missing at random mechanism. The SAS® procedure PROC MI will be used for the MCMC imputation of 100 complete data sets. Then, imputation will proceed with The SAS code for obtaining the imputed data is:

```

PROC MI DATA = INDATA SEED = 2568716 OUT = OUTDATA NIMPUTE = 100
  MINIMUM = 0 MAXIMUM = 4 ROUND = 0.5;
  BY TREATMENT;
  MCMC INITIAL = EM;
  VAR BASELINE IFS4 IFS5;
RUN;

```

where

- *INDATA* is the name of the input dataset
- *OUTDATA* is the name of the output dataset
- *TREATMENT* is the name of the treatment group variable

- *BASELINE* is the baseline inferior corneal fluorescein staining
- *IFS4-IFS5* are the inferior corneal fluorescein staining at Visits 4 (Day 15) through 5 (Day 29)

If MCMC multiple imputation fails to generate imputations, baseline total eye fluorescein staining score will be added to the `VAR` statement and multiple imputation will be reattempted. If MCMC multiple imputation still fail to generate the required imputation, then `MINIMUM`, `MAXIMUM`, and `ROUND` statements will be removed.

Tipping point analyses will be included for further sensitivity analyses. The SAS® procedure `PROC MI` will be used to impute non-monotone missing data using MCMC to obtain 100 complete datasets with a monotone missing pattern as described for the control-based pattern mixture model imputation. Then, the monotone datasets will be imputed using a set of shift values for the active treatment group. The set of shift values for the imputation will be from 0 to 4 by 0.1 increments. The SAS® code for obtaining the imputed data is:

```

PROC MI DATA = INDATA SEED = 935769 OUT = MDATA NIMPUTE = 100
      MINIMUM = 0 MAXIMUM = 4 ROUND = 0.5;
      BY TREATMENT;
      MCMC IMPUTE=MONOTONE;
      VAR BASELINE IFS4 IFS5;
      RUN;

PROC MI DATA = MDATA SEED = 427586 OUT = OUTDATA NIMPUTE = 1
      MINMAXITER = 1000000 MINIMUM = . 0 0 0 MAXIMUM = . 4 4 4
      ROUND = . 0.5 0.5 0.5;
      BY _Imputation_;
      CLASS TREATMENT;
      MONOTONE REG (IFS5 = BASELINE IFS4/DETAILS);
      MONOTONE REG (IFS4 = BASELINE /DETAILS);
      MNAR ADJUST (IFS5/ SHIFT = X ADJUSTOBS = (TREATMENT = 'ACTIVE
      TREATMENT') );
      VAR BASELINE IFS4 IFS5;
      RUN;

```

where

- *INDATA* is the name of the input dataset
- *MDATA* is the name an intermediary dataset with a monotone missing pattern
- *OUTDATA* is the name of the output dataset

- *TREATMENT* is the name of the treatment group variable
- *BASELINE* is the baseline inferior corneal fluorescein staining
- *IFS4-IFS5* are the inferior corneal fluorescein staining at Visits 4 (Day 15) through Visit 5 (Day 29)
- *X* is the shift parameter within the set of shift parameters [0 to 4 by 0.1]

Least squares mean differences, SEs, two-sided CIs and p-values will be reported for each shift value.

Further, primary efficacy analyses will be performed with the PP population with observed data only for sensitivity analysis. The following SAS® code is an example of the ANCOVA model for observed data, LOCF, and PP analyses:

```
PROC MIXED;
  CLASS TREATMENT SITE;
  MODEL CHG = BASELINE TREATMENT SITE / SOLUTION COVB;
  LSMEANS TREATMENT / CL PDIFF;
RUN;
```

Two sample t-tests will be conducted as sensitivity analyses using pattern mixture model imputation with the ITT population, observed data only with the ITT population, LOCF imputation with the ITT population, MCMC imputation with the ITT population, and observed data only with the PP population. Wilcoxon rank sum tests will be conducted as sensitivity analyses using observed data only with the ITT population, LOCF imputation with the ITT population, and observed data only with the PP population.

LS Means for inferior corneal fluorescein staining changes from baseline pre-CAE® and post-CAE® at Visit 5 (Day 29) will be displayed graphically in a bar chart with 95% CI bars by treatment group based on the ANCOVA analysis of the pattern mixture model imputation with the ITT population.

13.1.2 OCULAR DISCOMFORT SCALE AT VISIT 5 (DAY 29) Post-CAE, [REDACTED] K-161 [REDACTED] vs VEHICLE [REDACTED]

Ocular discomfort scores will be subjectively graded by the subjects using the Ora Calibra® Ocular Discomfort Scale at all visits at pre-CAE® and post-CAE® for each eye separately. The Ocular Discomfort Scale ranges from 0 to 4 where 0 = No Discomfort, 1 = Intermittent Awareness, 2 = Constant Awareness, 3 = Intermittent Discomfort, and 4 = Constant Discomfort. Analyses will only be produced for the study eye.

Ocular discomfort will be summarized at Visit 5 (Day 29) Post-CAE® by treatment groups using continuous descriptive statistics. Primary analysis will use an ANCOVA model adjusted for baseline ocular discomfort, site, and with treatment group as the explanatory variable. Changes from baseline for each treatment group in ocular discomfort will be compared between [REDACTED] K-161 [REDACTED] and vehicle [REDACTED]. In addition, treatment by baseline and treatment by study site interactions will be explored in separate models to evaluate how the treatment effect may differ for baseline value and study sites. In the case of a significant interaction at the 0.05 level, analyses will be performed by baseline stratification (≤ 3.0 and > 3.0) and/or site to understand how the treatment effect differs for baseline value and study sites. Least squares means for each treatment

group and the LS mean difference between treatment groups will be presented from the models together with SE, two-sided p-values, and two-sided 95% CIs.

The primary analysis will use control-based pattern mixture model imputation on the ITT population at Visit 5 (Day 29). SAS® code for the multiple imputation analysis will resemble the code in Section 13.1.1 for inferior corneal fluorescein staining. The random number seeds for the monotone imputation and pattern mixture model imputation described in Section 13.1.1 will be SEED = 354846 and SEED = 956546, respectively. In addition, the rounding parameter will be ROUND = 1.

Should control-based pattern mixture model imputation fail to produce the required imputations, baseline measurements of overall ocular discomfort, burning, dryness, grittiness, and stinging from the Ora Calibra® Ocular Discomfort & 4-Symptom Questionnaire will be added to the VAR statement in an iterative fashion until imputation is successful. If multiple imputation still fail to generate the required imputations, then MINIMUM, MAXIMUM, and ROUND statements will be removed.

Sensitivity analyses will be performed using on the ITT population using observed data only and ITT population using LOCF.

Sensitivity analyses under the assumption of a missing at random mechanism will be performed using MCMC imputation on the ITT population as described in section 13.1.1 except the random number seed for PROC MI will be SEED = 146645 and the rounding parameter will be ROUND = 1.

Should MCMC imputation fail to produce the required imputations, baseline measurements of overall ocular discomfort, burning, dryness, grittiness, and stinging from the Ora Calibra® Ocular Discomfort & 4-Symptom Questionnaire will be added to the VAR statement in an iterative fashion until imputation is successful. If MCMC multiple imputation still fail to generate the required imputation, then MINIMUM, MAXIMUM, and ROUND statements will be removed.

Tipping point analysis will be included for further sensitivity analyses in the manner described in section 13.1.1. Then, the monotone datasets will be imputed using a set of shift values for the active treatment group. The random number seeds for the monotone imputation and pattern mixture model imputation described in Section 13.1.1 will be SEED = 5324652 and SEED = 236135, respectively. The set of shift values for the imputation will be from 0 to 4.0 by 0.1 increments. The MINIMUM, MAXIMUM, and ROUND statements will be removed.

Further, primary efficacy analyses will be performed with the PP population with observed data only for sensitivity analysis.

Two sample t-tests will be conducted as sensitivity analyses using pattern mixture model imputation with the ITT population, observed data only with the ITT population, LOCF imputation with the ITT population, MCMC imputation with the ITT population, and observed data only with the PP population. Wilcoxon rank

sum tests will be conducted as sensitivity analyses using observed data only with the ITT population, LOCF imputation with the ITT population, and observed data only with the PP population.

Least squares means for Ocular Discomfort Score changes from baseline pre-CAE® and post-CAE® at Visit 5 (Day 29) will be displayed graphically in a bar chart with 95% CI bars by treatment group based on the ANCOVA analysis of the multiple pattern mixture model imputation of the ITT population.

